13.1.3 Therapy after End of Protocol Treatment

Therapy during the follow-up period will be according to current guidelines and is at the discretion of the investigator, regardless of whether the protocol treatment could be completed as planned or had to be discontinued prematurely). The treatment with everolimus/ribociclib can be extended in case of missing progress. The drug will be supplied by Novartis on study terms for the duration of the individual study participation (including 2-year-period of follow-up assessments). In case of clinical benefit the treatment with eribulin can be continued until progression of disease; the study drug will be (within the off-label use) supplied by Eisai as well.

13.2 Premature Termination of Study Participation in Single Patients

Study participation is terminated prematurely with single patients

- On the patient's request
- If in the investigator's opinion further participation would jeopardize the patient in an unjustifiable way.
- If a pregnancy is ascertained (applicable for eribulin cohort only)

If participation is terminated during the treatment period every effort should be taken to perform the conclusion visit of the randomized treatment period (cf. section 9.1). The obtained patient informations will be analysed. Data which are not necessary for study analysis will be destroyed.

13.3 Discontinuation or Premature Termination of Study in Single Sites

The sponsor, the coordinating investigator, the principal investigators, and the concerned competent authorities are reserved the right to initiate discontinuation or premature termination of the clinical trial in a single study site for the following reasons:

- Identification of a safety risk for the clinical trial participants of a single clinical trial center
- Non-compliance with the principles of GCP
- Insufficient recruitment
- Financial problems

If such action is considered, it is discussed with the principal investigator in advance.

If such action is taken the investigators and the principal investigator at the concerned trial center, the coordinating investigator and the sponsor must be informed immediately. It is the duty of the sponsor to notify the competent authority and the competent ethics committee within 15 days after premature termination or discontinuation. The principal investigator at the concerned center is to inform the local authority within the same time frame.

Furthermore, the clinical trial participants at the concerned trial center must be informed immediately about the discontinuation or termination. The investigator must ensure that the participants of the concerned study site are treated and followed-up appropriately. Date and time of the last application of the investigational drug as well as date and reason for the discontinuation or premature termination are to be documented in the participants' medical records and on the eCRFs.

In case of permanent discontinuation, all study materials (e.g. completed, partly completed and empty eCRFs) must be sent to the sponsor.

13.4 Premature Discontinuation of the Entire Study

The sponsor, coordinating investigator and the competent authorities may discontinue or terminate the entire study for the following reasons:

- Identification of a safety risk for the clinical trial participants
- Identification of problems with the trial design
- Non-compliance with the principals of GCP
- Insufficient recruitment of trial participants
- Financial problems

In consultation with the DSMB and the principle investigator the study should be discontinued by the sponsor, represented by [name]. [name], due to safety concerns if any of the following reasons are present:

If due to unexpected events the continuation of the study is not acceptable (ethical, medical or pharmaceutical legal aspects). This will be particularly the case,

- If any grade 4 toxicity occurs in > 20 % of the patients.
- If febrile neutropenia (defined as grade 3 or 4 neutropenia + fever > 38.5 C°) occurs in > 20 % of the patients.
- If grade 4 neutropenia occurs in > 20 % of the patients.
- If an unexpected amount of SUSARs occurs.
- If hand-foot-syndrome grade 4 occurs in > 30 % of the patients.

In the event of study termination, steps will be taken to ensure subjects transition smoothly off study, and if the risk/benefit profile is deemed to be appropriate, subject may continue to receive study treatments at the discretion of the investigator.

All investigators and the sponsor must immediately be informed about the discontinuation or premature termination. The principal investigator at each study site must notify the local competent authority within 15 days after premature termination. The sponsor is to notify the competent authority and the competent ethics committee within the same time interval.

Furthermore, all clinical trial participants must be informed immediately about discontinuation or premature termination. The responsible investigators must ensure that the clinical trial participants are treated and followed up appropriately. Date and time of the last application of the investigational medicinal product as well as date and reason for the discontinuation or premature termination are to be documented in the participants' medical records and on the eCRFs.

In case of permanent discontinuation, all study materials must be sent to the sponsor.

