3. Current active hepatitis B or C, clinically relevant known liver dysfunction, e.g. according to Child Pugh Classification class B and C, or biliary disease (with exception of patients with Gilbert's syndrome, asymptomatic gall-stones, liver metastases or stable chronic non-viral liver disease per investigator assessment).	
4. Concurrent disease or condition that might interfere with adequate assessment or evaluation of study data, or any medical disorder that would make the patient's participation unreasonably hazardous.	
5. Other malignant diseases within the last 3 years (apart from carcinoma in situ of the cervix or non-melanoma skin cancer)	
6. Dementia, altered mental status, or any psychiatric or social condition which would prohibit the understanding or rendering of informed consent or which might interfere with the patient's adherence to the protocol.	
7. Life expectancy < 3 months.	
8. Male gender.	
Everolimus/ribociclib cohort (DIVa)	Eribulin cohort (DIVb)

• Known hypersensitivity to any of the excipients of ribociclib, everolimus or any of the other given drugs.• Known hypersensitivity to lecithin (soya) and peanuts (ribociclib-cohort)• Disease or condition, which might restrain the ability to take or resorb oral medication. This includes malabsorption syndrome, requirement for intravenous (IV) alimentation, prior surgical procedures affecting absorption (for example resection of small bowel or stomach), uncontrolled inflammatory GI disease (e.g., Crohn's disease, ulcerative colitis) and any other diseases significantly affecting gastrointestinal function as well as inability to swallow and retain oral medication for any other reason.	
• History of hypersensitivity reactions attributed to eribulin.• Pre-existing neuropathy grade 3 or higher.• Severe Congenital long QT syndrome.• Pregnancy or nursing.

There will be NO EXCEPTIONS to eligibility requirements at the time of recruitment into the study. Questions about eligibility criteria should be addressed PRIOR to requesting recruitment.

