Everolimus is an immunosuppressant. Patients taking everolimus are therefore at an increased risk of infection. In oncology patients, some infections have been severe and rarely have had a fatal outcome. Physicians should be aware of the increased risk of infection, and should warn patients and their caregivers to be vigilant for signs and symptoms of infection, and to seek medical attention immediately should such signs or symptoms occur. Should an infection occur, anti-infectives should be prescribed as clinically appropriate, and in the case of clinically significant infection, consideration should be given to withholding study medication until resolution of the infection.

Management of hyperlipidemia and hyperglycemia

Treatment of hyperlipidemia should take into account the pre-treatment status and dietary habits. Blood tests to monitor hyperlipidemia must be taken in the fasting state. Grade 2 or higher hypercholesterolemia (>300 mg/dL or 7.75 mmol/L) or Grade 2 or higher hypertriglyceridemia (>2.5 x ULN) should be treated with a statin (HMG-CoA reductase inhibitor), fibrate, or appropriate lipid-lowering medication in addition to diet. Patients should be monitored clinically and through serum biochemistry as required in the product label/data sheets for HMG-CoA reductase inhibitors.

Note: Concomitant therapy with fibrates and HMG-CoA reductase inhibitors are associated with an increased risk of a rare but serious skeletal muscle toxicity manifested by rhabdomyolysis, markedly elevated creatine kinase (CPK) levels and myoglobinuria, acute renal failure and sometimes death. The risk versus benefit ratio should be determined for individual patients based on their risk of cardiovascular complications of hyperlipidemia.

Hyperglycemia has been observed in patients receiving everolimus therapy. Monitoring of fasting serum glucose is recommended prior to the start of everolimus therapy and periodically thereafter. Optimal glycemic control should be achieved before starting trial therapy.

Management of diarrhea

Appearance of diarrhea attributed to everolimus toxicity may be treated with Loperamide. Other medications for diarrhea may be used as needed.

Management of non-infectious pneumonitis

Clinically significant pneumonitis is typically accompanied by non-specific symptoms including dyspnea, non-productive cough, fatigue and fever.

Worst Grade	Recommended Investigations	Management of Pneumonitis	Everolimus Dose Adjustment

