11 ADVERSE EVENT REPORTING

11.1 Definitions, Collection and Recording of Adverse Events by the Investigator

An adverse event (AE) is any untoward medical occurrence in a patient administered a pharmaceutical product and which does not necessarily have a causal relationship with this treatment. An adverse event (AE) can therefore be any unfavorable and unintended sign (including an abnormal laboratory finding), symptom, or disease temporally associated with the use of a medicinal (investigational) product, whether or not related to the medicinal (investigational) product. In particular this includes new findings or changes from baseline in laboratory test results or any other safety assessments (e.g. ECGs, radiological scans, vital signs assessments) felt to be clinically significant in the medical and scientific judgment of the investigator.

During treatment period AEs are collected by the investigator at least on every visit of the patient at the study site, whether it is a scheduled study visit or not.

During the follow-up period (after conclusion of the treatment period) only adverse events are collected by the investigator which are \geq grade 3 NCI CTCAE and/or serious.

Every adverse event is followed up until it has subsided or stabilized.

On each AE the following data are raised and documented by the investigator in the respective electronic case report form:

- Diagnosis or each single symptom if diagnosis is not available,
- Date and time of onset and end of AE,
- Whether onset was after the first administration of study medication (yes/no),
- Course (continuous / intermittent, if intermittent: number of episodes),
- Whether the AE is a reportable serious adverse event (serious/ non-serious, for the definition of "reportable serious event" cf. section 1.3),
- Intensity (grade 1 to 5 according to the NCI Common Terminology Criteria for Adverse events (CTCAE) version 4.03),
- Causal relationship with investigational medicinal product (no (not related) / yes (reasonable possibility)),
- Counter-measures (none/ dose reduced/ drug withdrawn/ other drug treatment/ other measures),
- Outcome (recovered/ recovering/ not recovered/ recovered with sequelae/ fatal/ unknown),

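### The severity-based stopping counts in section 13.4 name grade 4 but not grade 5, so read literally a patient whose event is graded only 5 is not counted

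*Protocol*

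**What the plan says.** Section 13.4 says that the study should be discontinued for safety when its continuation is no longer acceptable, and lists cases in which this particularly applies. Four of them are numeric:

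- The general line: "If any grade 4 toxicity occurs in > 20 % of the patients".
- A line for febrile neutropenia, with the same 20% limit, defined through neutropenia of grade 3 or 4 together with fever.
- A line for neutropenia of grade 4 taken alone, again with a 20% limit.
- A line for one skin toxicity, at a higher limit: "If hand-foot-syndrome grade 4 occurs in > 30 % of the patients".

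A fifth item has no number: "If an unexpected amount of SUSARs occurs".

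Section 11.1 fixes the scale on which each adverse event is recorded: "Intensity (grade 1 to 5 according to the NCI Common Terminology Criteria for Adverse events (CTCAE) version 4.03".

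Section 15.4 links the two. A safety analysis follows recruitment of 15 patients, and recruitment continues during it unless the section 13.4 thresholds are exceeded or the DSMB recommends otherwise in extenuating circumstances.

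Fatal reactions are foreseen. Section 3.2.7 mentions an occasional death from everolimus pneumonitis. Section 8.2.3.1 says of infections under everolimus: "In oncology patients, some infections have been severe and rarely have had a fatal outcome".

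**The concern.** Grade 5 is the fatal grade, one step above the highest grade that any section 13.4 line names. The protocol writes a floor where it means one. The eribulin exclusion criterion is "Pre-existing neuropathy grade 3 or higher". Section 8.3.3 sets a floor at grade 2 for renal impairment, and section 9.2 a floor at grade 3 for events collected in follow-up. Section 13.4 does not use this form, so a person applying it as written counts grade 4 only.

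The count then ranks outcomes the wrong way round: a survived grade 4 event moves it towards the limit, and death from the same event does not. The SUSAR item does not clearly fill the gap. It carries no number, and section 11.4 defines unexpected as not listed in the German product information, so a known reaction that proves fatal may fall outside it. At stake is whether the one rule-based trigger for suspending recruitment responds to the worst outcome.

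**Working it through.** **Status of the 20% limit.** It is a chosen cut-off. The protocol attaches no expected rate or operating characteristic to it, so there is no stated figure to reproduce. What can be checked is the number of patients it implies and which events enter that number.

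**Inputs.** Limit: more than 20% of patients (section 13.4). First review: 15 patients (section 15.4). Planned enrolment: 90 on everolimus, 90 on ribociclib and about 120 on eribulin (section 15.3), which makes 180 in the everolimus/ribociclib cohort and 300 in total.

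**Step 1: patients needed to exceed the limit,** floor(0.20 × n) + 1.

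| n | 0.20 × n | Patients needed | Share when exceeded |
|---|---|---|---|
| 15 | 3 | 4 | 26.7% |
| 90 | 18 | 19 | 21.1% |
| 120 | 24 | 25 | 20.8% |
| 180 | 36 | 37 | 20.6% |
| 300 | 60 | 61 | 20.3% |

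The number needed is the same whether or not grade 5 is counted. Only what enters the numerator changes.

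**Step 2: the same 15 patients counted two ways.** Take three patients with a grade 4 event and one other patient whose only qualifying event is graded 5, pooling all toxicities.

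- As written: 3/15 = 20.0%, not more than 20%, limit not exceeded.
- With grade 5 counted: (3 + 1)/15 = 4/15 = 26.7%, limit exceeded.

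**Step 3: how far the two counts can diverge (assumed rates only).** The protocol gives no expected grade 4 or grade 5 rate for its cohorts, so the rates here are illustrations. Let X be the number of counted patients, X ~ Binomial(n, p). As written, p is the grade 4 rate. With grade 5 counted, p is the sum of the two rates, taking the events to fall in different patients. The chance of exceeding the limit is P(X ≥ 4) at n = 15, P(X ≥ 19) at n = 90 and P(X ≥ 25) at n = 120.

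| Assumed grade 4 / grade 5 rate | n | As written | Grade 5 counted |
|---|---|---|---|
| 15% / 0% | 15 | 0.177 | 0.177 |
| 15% / 5% | 15 | 0.177 | 0.352 |
| 15% / 10% | 15 | 0.177 | 0.539 |
| 15% / 10% | 90 | 0.074 | 0.835 |
| 15% / 10% | 120 | 0.053 | 0.878 |

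With no grade 5 events the two counts agree. The more of the severe toxicity that is fatal, the less the written count responds. The reversed ordering itself rests on the wording and needs no assumed rate.

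**The case against.** The strongest reply is that section 13.4 is not a closed algorithm. Its numeric lines illustrate a general clause, and the same section allows stopping for any identified safety risk. Under section 15.4 the 15-patient review covers all reported serious events, is not confined to events with a stopping rule, and leaves the DSMB free to recommend suspension. Section 11.4 adds that a single expected serious reaction with an unexpected outcome, such as death, is reportable as an issue that may require the risk-benefit balance to be reassessed.

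All of this stands. A reader might infer that a fatal reaction cannot stop the study, that each uncounted death reverses the decision, or that the protocol has no provision for fatal outcomes. The documents support none of these readings. The DSMB would see the death and is not bound by the count.

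Three narrower points also stand:

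- A fatal febrile neutropenia still counts if its grade 3 or 4 neutropenia and fever were recorded. A patient with a separately recorded grade 4 event counts too. The gap concerns events graded only 5.
- The three-plus-one example sits at the edge of the limit and pools all grade 4 toxicities. If the general line means any one given toxicity, the example needs all four events to be of the same kind. The text does not settle which is meant, but the omission of grade 5 is present either way.
- Section 17.12 refers to DSMB operating procedures that are not shown and may say how deaths are handled.

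What the reply does not do is bring grade 5 into the count. The safeguards rest on judgement or on reporting, while the count is the rule-based trigger that section 15.4 relies on.

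**Conclusion.** The point holds as a defect in the pre-specified count and no further. No severity-based line in section 13.4 covers grade 5, although section 11.1 records it and section 15.4 uses the thresholds to decide on suspending recruitment. At 15 patients one uncounted fatal event is enough to separate 20.0% from 26.7%, on two assumptions: grade 4 toxicities are pooled, and the patient who died has no separately recorded grade 4 event. The probabilities in the working rest on invented rates and show direction only.

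The practical risk is reduced, but not removed, by the discretionary safeguards. It is worth correcting because the rule concerns patient safety and the correction is small.

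**What to change.** The sponsor and DSMB should reconcile sections 13.4, 11.1 and 15.4 so that the severity counts in section 13.4 state explicitly that they cover grade 5 as well as grade 4 events. The percentage limits stay as they are. The clarification should not add a relatedness qualifier or a new rule for holding recruitment: either would be a change of substance, and the point does not require it.

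The cost is a few words in section 13.4. Grade 5 is already recorded under section 11.1, so no new data are needed.

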Other toxicities	
Grade 1: It toxicity is tolerable, no dose adjustment required.
 
Grade 2: It toxicity is tolerable, no dose adjustment required. It toxicity becomes intolerable, interrupt everolimus until resolution to \leq grade 1. Restart at the same dose. If toxicity recurs at grade 2, interrupt dose until recovery to grade \leq 1. Restart at a lower dose.
 
Grade 3: Interrupt everolimus until recovery to grade \leq1. Reintroduce everolimus at the next lower dose level
 
Grade 4 Discontinue everolimus treatment

Toxicity requiring interruption for >4 weeks	Permanently discontinue treatment.

No specific dose adjustments are recommended for Grade 1 toxicity. However, physicians should always manage patients according to their medical judgment based on the particular clinical circumstances.

Table 15: Everolimus dose modification guidelines for non-hematologic toxicities

Toxicity	Actions
Thrombocytopenia	
 $\geq 75000/\text{mm}^3$: No change
Platelet count	
 $50000/\text{mm}^3$ to $75000/\text{mm}^3$ Hold everolimus treatment until recovery to $\geq 75000/\text{mm}^3$ Reintroduce everolimus at the same dose level $< 50000/\text{mm}^3$ Hold everolimus treatment until recovery to $\geq 75000/\text{mm}^3$ Reintroduce everolimus at the next lower dose level, if available.
Absolute Neutrophil count (ANC)	
 $\geq 1000/\text{mm}^3$: No change $500/\text{mm}^3$ to $1000/\text{mm}^3$ Hold everolimus treatment until recovery to $\geq 1000/\text{mm}^3$ Reintroduce everolimus at the same dose level $< 500/\text{mm}^3$ Hold until recovery to $\geq 1000/\text{mm}^3$. Reintroduce everolimus (at the next lowest dose level, if available).
Febrile neutropenia	Hold further dosing until ANC $\geq 1250/\text{mm}^3$ and no fever. Then resume dosing at the next lower dose level, if available.
Toxicity requiring interruption for > 4 weeks	Permanently discontinue everolimus treatment

Physicians should always manage patients according to their medical judgment based on the particular clinical circumstances.

Table 16: Everolimus dose modification guidelines for hematologic toxicities

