Thrombocytopenia		
 Grade 1 ($\geq 75 \times 10^9$): No change
Platelet count		
 Grade 2 ($50 \times 10^9 - 75 \times 10^9$) Dose interruption until recovery to grade ≤ 1 Reintroduce ribociclib at the same dose level Grade 3 ($25 \times 10^9 - 50 \times 10^9$) Dose interruption until recovery to grade ≤ 1 Reintroduce ribociclib at the same dose level If toxicity recurs at grade 3: temporary dose interruption until recovery to grade ≤ 1 and reduce ribociclib to the next lowest dose level. Grade 4 ($<25 \times 10^9$) Dose interruption until recovery to grade ≤ 1 Reintroduce ribociclib at the next lower dose level. If toxicity recurs at grade 4: discontinue ribociclib.
Absolute Neutrophil count (ANC)	Neutrophil count	
 Grade 1 ($\geq 1,5 \times 10^9$): No change Grade 2 ($1,5 \times 10^9 - 10^9$): No change Grade 3 ($0,5 \times 10^9 - 1 \times 10^9$): Dose interruption until recovery to $\geq 1.0 \times 10^9/L$ Reintroduce ribociclib at the same dose level. If toxicity recurs at grade 3: temporary dose interruption until recovery to $\geq 1.0 \times 10^9/L$ If resolved in ≤ 7 days, then maintain dose level. If resolved in > 7 days, then reduce ribociclib dose to the next lower dose level. Grade 4 ($<0,5 \times 10^9$): Dose interruption until recovery to $\geq 1.0 \times 10^9/L$ Reintroduce ribociclib at the next lower dose level. If toxicity recurs at grade 4: temporary dose interruption until recovery to $\geq 1.0 \times 10^9/L$ And reduce ribociclib at the next lower dose level.
Febrile neutropenia		
 Grade 3 (ANC $< 1.0 \times 10^9/L$ with a single temperature of $> 38.3^\circ C$ or a sustained temperature of $\geq 38^\circ$ for more than one hour): Dose interruption until improvement of ANC $\geq 1.0 \times 10^9/L$ and no fever. Restart at the next lower dose level. If febrile neutropenia recurs, discontinue ribociclib. Grade 4 (Life-threatening consequences; urgent intervention indicated): Discontinue ribociclib.
Anemia (Hemoglobin)		
 Grade 1 ($\geq 10.0 \times LLN$ g/dl): No change Grade 2 ($\geq 8.0 - < 10 \times LLN$ g/dl): No change Grade 3 ($< 8.0 \times LLN$ g/dl):

Dose interruption until recovery to grade ≤ 2 .

Reintroduce ribociclib at the same dose.

• **Grade 4 (Life-threatening consequences; urgent intervention indicated):**

Discontinue ribociclib

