8.4.2.1 Permitted study drug dose adjustments and interruptions

Treatment with eribulin should continue as long as clinical benefit is observed or until unacceptable toxicity occurs. Management of severe and/or intolerable suspected adverse events may require temporary dose reduction and/or interruption.

For patients who do not tolerate the protocol-specified eribulin dosing schedule, dose adjustments are permitted in order to allow the patient to continue the study. The following guidelines need to be applied: Dose adjustments are permitted for any adverse event suspected to be related to eribulin in those patients unable to tolerate the normal dose. If administration of eribulin must be interrupted because of unacceptable toxicity, eribulin dosing will be interrupted or modified according to the guidelines in TABLE 15 below.

All study drug interruptions or dose modifications must be recorded on the Dosage Administration Record page of the eCRF.

For patients who are unable to tolerate the protocol-specified dosing scheme, dose adjustments and interruptions are permitted in order to keep the patient on the study drugs. The following guidelines should be followed.

The administration of eribulin should be delayed on Day 1 or Day 8 for any of the following:

- Absolute neutrophil count (ANC) < 1000/μl
- Platelets < 75000/μl
- Grade 3 or 4 non-hematological toxicities.

Patients who interrupt eribulin therapy for more than 4 weeks must be discontinued from the study.

Dose reduction during therapy

Dose reduction recommendations for retreatment are shown in the following TABLE 24.

Adverse reaction after previous eribulin administration	Recommended dose of eribulin
Haematological:	
ANC < 0.5 x 10 ⁹ /l lasting more than 7 days	0.97 mg/m²
ANC < 1 x 10 ⁹ /l neutropenia complicated by fever or infection	
Platelets < 25 x 10 ⁹ /l thrombocytopenia	
Platelets < 50 x 10 ⁹ /l thrombocytopenia complicated by haemorrhage or requiring blood or platelet transfusion	
Non-haematological:	
Any Grade 3 or 4 in the previous cycle	
Reoccurrence of any haematological or non-haematological adverse reactions as specified above:	
Despite reduction to 0.97 mg/ m ²	0,62 mg/m²
Despite reduction to 0.62 mg/m ²	Consider discontinuation

Table 24: Eribulin dose modification guidelines for toxicities.

Do not re-escalate the eribulin dose after it has been reduced.

Patients with hepatic impairment

Impaired liver function due to metastases:

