15.4 Safety Analysis

The assessment of safety will be based mainly on the frequency of adverse events. Other safety data (e.g. laboratory values, vital signs, and special tests) will be considered as appropriate. For all safety analyses, the safety set will be used. A safety analysis will be performed by the coordinating investigator and the DSMB after recruitment of 15 patients. Steps will be taken to preserve data confidentiality and to ensure the scientific integrity of the ongoing study. The safety analysis will be conducted on all patients who received at least one dose of the study treatment. Recruitment will not be suspended while this safety analysis is undertaken, except if the stopping thresholds specified above (cf. Premature Discontinuation) are exceeded or on recommendation of the safety review committee (DSMB) for extenuating circumstances (e.g. delay in data retrieval or analysis, emerging unforeseen safety concerns). Every effort will be made to minimize the time from the analysis cut-off date to data retrieval, analysis, and safety review decision. In case of unexpected toxicity the advisory board and the DSMB will be informed and give their advisory vote. Based on the recommendations of this team, a protocol amendment may be implemented to modify dose or study procedures. The safety review is not limited to these adverse events for which stopping rules are established; in the event that other safety concerns are identified, the study could also be closed. All SAEs which are reported to the Sponsor as required by the protocol will be reviewed during this safety analysis. In addition to this safety analysis of the first cohort, ongoing individual events will be reviewed on an ongoing basis, according to routine protocol and pharmacovigilance procedures.

16 **PUBLICATION POLICY**

The results of this study will be published. The responsibility is with the coordinating investigator.

17 **ETHICAL, REGULATORY AND ADMINISTRATIVE ISSUES**

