APPENDIX IV – NCI COMMON TERMINOLOGY CRITERIA FOR ADVERSE EVENTS VERSION 4.03 (CTCAE)

This study will utilize the NCI Common Terminology Criteria for Adverse Events Version 4.03 (CTCAE) for adverse events and serious adverse event reporting. A copy of the CTCAE Version 4.03 can be downloaded from the CTEP home page: http://evs.nci.nih.gov/ftp1/CTCAE/CTCAE_4.03_2010-06-14_QuickReference_5x7.pdf

Introduction

Possible prolongation of survival due to additional treatment with everolimus must be appraised in the light of contingent side effects, which may lower patients' quality of life. To evaluate eventual efficacy of everolimus, quality of life assessments are indispensable.

Instructions for Administration of a Quality of Life Questionnaire

The instructions below are intended as a guide for the administration of the Quality of Life questionnaire.

1. Preamble

Quality of life data are collected for research purposes, and will usually not be used for the patient's individual medical care. The assessment is in the form of a self report questionnaire. Therefore, it must be completed by the patient only, without translation, coaching or suggestions as to the "correct" answer by relatives or health care personnel.

If a particular question has not been answered, please document the reason(s) in the appropriate space on the questionnaire. If the whole questionnaire has not been completed, please document the reason(s) on the appropriate case report forms.

2. Pretreatment Assessment

It should be explained to the patient that the purpose of the questionnaire is to assess the impact of treatment on different areas of the patient's life, e.g.: psychological distress, social disruption, side-effects, et cetera.

The center CRA should collect the questionnaire as soon as it has been completed, check to see that each question has been answered and gently remind the patient to answer any inadvertently omitted questions. If a patient states that she prefers not to answer some questions and gives a reason(s), the reason(s) should be noted on the questionnaire. If a specific reason is not given, this also should be noted on the questionnaire.

3. Assessments During Treatment

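### For ribociclib patients the protocol defines febrile neutropenia in two conflicting ways: the study-level stop (section 13.4) needs a higher temperature than the dose table (Table 21), so some events that change dosing do not count toward the stop

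*Protocol*

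**What the plan says.** **Study-level stop.** Section 13.4 says the sponsor should discontinue the study, in consultation with the DSMB, if certain toxicities become too frequent. One criterion reads: "If febrile neutropenia (defined as grade 3 or 4 neutropenia + fever > 38.5 C°) occurs in > 20 % of the patients". The same list has separate 20% limits for grade 4 neutropenia and for any grade 4 toxicity.

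**Ribociclib dosing.** Table 21 (section 8.3.2.1) describes grade 3 febrile neutropenia as a neutrophil count below 1.0 x 10^9/L "with a single temperature of $> 38.3^\circ C$ or a sustained temperature of $\geq 38^\circ$ for more than one hour". Such a patient interrupts ribociclib and restarts one dose level lower. A recurrence ends ribociclib.

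**Other dose tables.** Table 16 (everolimus) names febrile neutropenia without a temperature: "Hold further dosing until ANC $\geq 1250/\text{mm}^3$ and no fever". Table 24 (eribulin) refers only to "neutropenia complicated by fever or infection".

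**Recording.** Section 11.1 has adverse events graded "according to the NCI Common Terminology Criteria for Adverse events (CTCAE) version 4.03". The items it lists for each event are diagnosis, dates, onset relative to first dose, course, seriousness, grade, causality, counter-measures and outcome. The temperature reached is not among them.

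**Use of the thresholds.** Section 15.4 keeps recruitment open during the safety analysis "except if the stopping thresholds specified above (cf. Premature Discontinuation) are exceeded" or the DSMB recommends otherwise.

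**The concern.** A stopping criterion should count the event the trial recognises under that name. Here one named event has two definitions, and the one that decides whether the study continues is the narrower. A ribociclib patient can be interrupted and dose-reduced for febrile neutropenia and still be absent from the febrile neutropenia count.

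Two things follow. The stopping count for ribociclib patients can equal the Table 21 count or fall below it, but never exceed it. And the section 13.4 count cannot be built from the event data listed in section 11.1, because a recorded diagnosis of febrile neutropenia does not show whether the temperature passed 38.5 °C. Body temperature is taken at scheduled visits (section 9.1), but these are two to four weeks apart and need not coincide with an episode.

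**Working it through.** **Step 1: compare the definitions.** Table 21 puts grade 3 neutropenia at 0.5 to 1.0 x 10^9/L and grade 4 below 0.5 x 10^9/L. Grade 3 or 4 neutropenia in section 13.4 is therefore the same range as the count below 1.0 x 10^9/L in the febrile neutropenia row. Only the temperatures differ. A fever above 38.5 °C is also above 38.3 °C, so every section 13.4 event meets Table 21. The reverse fails for a single reading above 38.3 and up to 38.5 °C, and for 38.0 to 38.5 °C sustained beyond one hour.

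| Ribociclib patient | Table 21 | 13.4 febrile neutropenia | Other 13.4 limit |
|---|---|---|---|
| Count 0.8, single 38.4 °C | yes | no | none |
| Count 0.8, 38.2 °C for two hours | yes | no | none |
| Count 0.4, single 38.4 °C | yes | no | grade 4 neutropenia; any grade 4 toxicity |
| Count 0.8, single 38.7 °C | yes | yes | none |

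The group that no numerical limit catches is mainly grade 3 neutropenia with fever up to 38.5 °C.

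**Step 2: which patients.** Only Table 21 states a temperature. For everolimus and eribulin, section 13.4 is the only numerical definition in the text, so there is nothing for it to contradict. Section 15.3 plans 90 ribociclib patients, recruited after the first 90 DIVa patients, who receive everolimus.

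**Step 3: size, as an illustration.** The protocol gives no operating characteristics for this rule, so there is no stated figure to reproduce. It also does not give the share of events lying between the two definitions. Assumptions:

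- n = 90, with the limit applied to the ribociclib group by itself;
- true rate by Table 21 of 25%, which is above the limit;
- uncounted share s of 0, 10, 25 or 40%.

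The limit: 0.20 x 90 = 18, so more than 20% means at least 19 patients. The chance of crossing it is P(X >= 19) for X binomial with n = 90 and p = 0.25 x (1 - s).

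| s | p | P(X >= 19) |
|---|---|---|
| 0% | 0.25 | 0.83 |
| 10% | 0.225 | 0.66 |
| 25% | 0.1875 | 0.32 |
| 40% | 0.15 | 0.07 |

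**Step 4: the protocol's own rates.** Section 3.3.9.3 reports febrile neutropenia in 1.5% with ribociclib plus letrozole. Table 25 gives 4.7% for eribulin. At either rate P(X >= 19 of 90) is zero to five decimals, with every event counted. Even among 15 patients, where 4 would be needed, the chance is 0.00006 and 0.004. The mismatch affects the decision only if the true rate is near or above 20%.

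**The case against.** The strongest reply is that section 13.4 states its definition in full where it is used, so the trigger is not ambiguous. Closing a trial and adjusting one patient's dose are different decisions, and a stricter threshold for the first may be deliberate. That is possible, but the protocol nowhere says so. It uses the same name for both events, and it does not list the temperature as an item to record.

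The criterion is also not the only safeguard. The grade 4 limits catch patients with counts below 0.5 x 10^9/L at any temperature. The section 13.4 list is open-ended. Section 15.4 says the safety review is not confined to events with stopping rules, and it covers all SAEs reported to the sponsor. These points stand. They narrow the gap but do not remove the contradiction.

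A reader might infer that the whole trial's stopping count is too low, including at the safety analysis after 15 patients and in the 120-patient eribulin cohort. The documents do not support that. On the planned sequence the first DIVa recruits receive everolimus, so those 15 patients would include none on ribociclib, and Table 21 does not apply to eribulin. Extending the conflict to these patients would need the CTCAE 4.03 definition of febrile neutropenia, which Appendix IV does not reproduce. It says only "This study will utilize the NCI Common Terminology Criteria for Adverse Events Version 4.03 (CTCAE) for adverse events and serious adverse event reporting" and gives a link.

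**Conclusion.** The inconsistency is real and confined to the ribociclib group. Its direction is certain: the section 13.4 count cannot exceed the Table 21 count and may fall short of it. Its size is unknown, because the protocol does not say how many events lie between the two temperatures. The fall from 0.83 to between 0.66 and 0.07 rests on three assumptions: a 25% true rate, 10 to 40% of events uncounted, and a limit applied to 90 ribociclib patients alone. It shows what could happen if toxicity were far worse than expected and is not a forecast. At the rates the protocol cites, neither definition would be likely to trigger the stop.

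The point is still worth correcting, since a stopping rule exists for toxicity beyond expectation and the repair is small. Nothing here shows which temperature is right.

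**What to change.** Reconcile section 13.4 with Table 21 in one of two ways:

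- let one stated definition of febrile neutropenia govern both ribociclib dosing and the stopping count; or
- state that the difference is intended, and record for each event the temperature (and duration, if needed) required to apply the section 13.4 definition.

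The choice of temperature belongs to the sponsor and its clinical advisers.

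The first option costs a line of text. The second costs a sentence and one or two eCRF items. Neither changes the sample size, the visit schedule or the planned analyses.
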